### 7.1. Sample Size Calculation

There is no active de novo patient enrollment in this study and all women in the database who meet the inclusion criteria during the recruitment period will be included in the analysis. Therefore, the focus of the sample size calculation was to determine the precision of the estimated incidence rate ratios (IRR) that can potentially be achieved in the study depending on several different hypothetical scenarios of subject accrual. Depending on drug uptake in the participating countries, speed of accrual, event rates, and actual dropout rates, the precision of the estimated incidence rate ratio may change.

The estimates are based on the expected incidence rate of VTE as the primary endpoint. It is estimated that the incidence rate of VTE in women who are not treated with a SERM or HT is 1.74/1000 patient-years (PY), based on data from the placebo groups in bazedoxifene clinical trials. It is assumed that women treated with raloxifene would have a higher incidence of VTE, of 2.17/1000 PY, based on data from the Phase III pivotal trials of bazedoxifene. The rate of VTE observed in the raloxifene arm of the bazedoxifene pivotal trials is lower than the rate reported in the Multiple Outcomes of Raloxifene Evaluation (MORE) trial [1]. In the MORE trial, the incidence rate of VTE was 3.5/1000 patient-years in women randomized to raloxifene. Therefore, our calculations are likely to be substantially more conservative than estimates based on rates in the literature.

All estimates (Table 3, Table 4) were calculated with two-sided 95% confidence intervals. According to the study plan, there will be a 3-year accrual period and each woman will be followed for up to 5 years from enrollment. Since osteoporosis therapies are chronic therapies, it is likely that women will be exposed to the drugs for more than one year. A conservative annual loss to follow up rate of 15% was used in the estimation. Estimates were based on Wald 95% confidence intervals [2]

**Table 3: 95% Confidence Intervals (CI) for Incidence Rate Ratios (IRR) with different numbers of patients in the BZA arm and the primary comparator arm**

Bazedoxifene (n)	Bisphosphonate (n)	BZA:Bisphosphonate	Underlying Incidence Rate Ratio (IRR)		
			1	1.5	2
			95% CI of observed point estimate of IRR		
2150	8600	1:4	0.6, 1.7	1.0, 2.4	1.3, 3.0
2000	8000	1:4	0.6, 1.8	0.9, 2.4	1.3, 3.1
1750	10,500	1:6	0.6, 1.8	0.9, 2.5	1.3, 3.1
1500	12,000	1:8	0.5, 1.9	0.9, 2.5	1.3, 3.2

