* Due to low enrolment/accrual into the study, the original end of the study accrual period was extended from September 30th 2012 in Spain, and April 30th 2013 in Italy, to April 30th 2014 for both Spain and Italy. Extending the accrual period to April 2014 extended the study timelines by 1 year. The new accrual period for Spain is 43 months (October 1st 2010-April 30th 2014) and the new accrual period for Italy is 36 months (May 1st 2011-April 30th 2014).

Patients will be counted in according to the inclusion criteria.

Follow up for each endpoint will be from the index date to whichever of the following occurs first.

1. Endpoint under investigation
2. Last patient visit or completion of 5 years follow up, whichever occurs first.

Each patient will be followed for identification of selected endpoints for a period of up to five years from their index prescription date for BZA, bisphosphonate or raloxifene. The follow up will continue even if the woman discontinues the index medication or switches to a different medication during this five year follow up period. The follow up duration of an individual patient may be shorter than five years if the woman transfers out of the GP office that wrote the index prescription or if she dies.¹ In these situations the data will be censored on the date of last visit. This study will use the Cegedim Longitudinal Patient Database (LPD), an electronic medical records database. However, the Spanish and Italian databases of Cegedim Strategic Data (CSD) do not have recorded events of death and date of death. The discontinued patient's record indicate loss to follow-up for various reasons, such as patients' moving from the areas, patient's change of GPs or other various reasons. The number of patients who are lost to follow-up will be provided. A minimum of a six month history in the LPD database prior to the index date (at least one GP visit, whatever the motive of the visit to GP) is required for inclusion of population, in order to ensure a certain quality of information.

Study Population

The study population will be selected based on the following inclusion criteria and all eligible patients enrolled in this study will be included. No exclusion criteria were applied.

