8.1.2 INCIDENCE RATES

Incidence rates will be calculated for all endpoints in all cohort groups; incidence rate ratios and 95% confidence intervals will be calculated as specified previously.

The incidence rate for all end points will be calculated using both the cumulative incidence approach and an incidence density (person-time) approach. The cumulative incidence approach will be used as the primary analysis and it will be calculated as in the following formula:

$$\text{Incidence rate} = (\text{Total new cases during follow-up period} / \text{Total persons at risk during follow-up period})$$

For this study, the numerator will be defined as the total number of patients with a diagnosis of primary end points or secondary end points during follow-up period. The denominator will be the total number of all patients at risk in cohorts groups during follow-up period.

Secondly, an incidence density approach calculates time at risk in person-years, measured from first prescription to the end of the observation period. The incidence rate will be reported as per 1,000 person-years of observation as shown in the following formula:

$$\text{Incidence Rate} = (\text{Total new cases during follow up period} / \text{Total person years during follow-up period}) * 1000$$

The numerator will be defined as the total number patients with end points of interest during follow-up period. The denominator will be defined as the sum of person years of patients during the follow up period. For patients who have incidence of primary or secondary end points, person time will equal the sum of days from their first prescription of treatment (index prescription) until the date of the incident condition (diagnosis of primary or secondary end points). For patients who do not experience an incidence of primary or secondary end points, person time will equal the sum of days from their first prescription of treatment (index prescription) to the last visit date or completion of 5 years follow up at which all patients will be censored, whichever occurs first.

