In the treatment of chronic conditions such as osteoporosis, patients may discontinue their study medication (BZA/bisphosphonate/raloxifene) or change study medications. Such exposure changes are often due to treatment failure or perceived/real side effects. The stronger such non-adherence is associated with the outcome; the more an as-treated (AT) analysis, which censors at the point of discontinuation, will be biased. A cumulative risk (CR) (similar to intention-to-treat analyses in randomized trials) analysis follows all patients for a fixed time period, carrying forward the initial exposure status and disregarding any changes in treatment status over time. Because this analysis disregards informative non-adherence, it will not suffer bias as a consequence of censoring, but it will suffer bias as a consequence of exposure misclassification. Such misclassification increases with a longer follow-up period and a shorter average time to discontinuation. In most cases, though not all, such misclassification will bias effects towards the null, similar to intention-to-treat analyses in randomized trials. Viewed separately, the AT and CR analyses trade biases, but together they give a range of plausible effect estimates. Adjusting for non-adherence in an analysis of a drug effect requires information about the predictors of treatment discontinuation, which is not available with sufficient accuracy in secondary data such as that used in this study [1].

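### The cumulative-risk analysis is described as free of censoring bias, but this holds only for censoring at treatment change: loss at last visit remains, is shared with the as-treated analysis, and shifts the crude cumulative incidence ratio when loss is unequal.

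*SAP*

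**What the plan says.** SAP 8.1.4, under the subheading on patients switching medications, contrasts two analyses. It says that the stronger the link between non-adherence and outcome, the more "an as-treated (AT) analysis, which censors at the point of discontinuation, will be biased". CR, by contrast, "follows all patients for a fixed time period" under the initial drug. "Because this analysis disregards informative non-adherence", the SAP continues, "it will not suffer bias as a consequence of censoring"; its stated weakness is exposure misclassification. Of the pair it says that "together they give a range of plausible effect estimates".

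The follow-up rules elsewhere are different:

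- SAP 2.1, on women who transfer out or die: "In these situations the data will be censored on the date of last visit". The same section says that the Spanish and Italian databases hold neither deaths nor death dates, and that the number lost will be given.
- SAP 8.1.2, on person-time for women without an event: it runs "to the last visit date or completion of 5 years follow up at which all patients will be censored, whichever occurs first". SAP 8.1.4 uses the same end point for time to event.
- SAP 8.1.2 makes cumulative incidence, computed as new cases divided by persons at risk, the primary incidence analysis. Incidence density comes second.
- Protocol 7.1, on planned loss: "A conservative annual loss to follow up rate of 15% was used in the estimation".

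**The concern.** The stated property of CR rests on fixed follow-up, and the plan does not deliver fixed follow-up. Carrying the first drug forward removes the censoring caused by stopping or switching. It does nothing about a woman who leaves the practice or dies, and 8.1.4 does not mention that second kind of censoring.

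The documents suggest a route by which such loss could be related to the outcome. SAP 2.1 says that hospital information enters the GP file at visits after discharge and is not collected systematically. A woman who dies of a pulmonary embolism in hospital makes no such visit. Unless the event reaches the file another way, she is censored event-free at her last visit. If she was on her first drug at the time, this happens in AT and CR alike.

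At stake is how the VTE comparison will be read. A report that follows 8.1.4 could present CR as free of censoring bias, and agreement between AT and CR as reassurance, when both depend on the same unexamined assumption about loss. Separately, a crude proportion gives a woman seen for one year the same denominator weight as a woman seen for five.

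**Working it through.** **Inputs.** From Protocol 7.1: VTE rate r = 1.74 per 1,000 person-years, 15% annual loss, up to 5 years of follow-up, and Table 3. From SAP 5.4: 1,823 bazedoxifene women. Loss rates other than 15%, fractions of unrecorded events and risk strata are assumptions and are labelled so.

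**1. The plan's own figures that use the 15% loss.** Section 8.1.4 states no figure. Table 3 can be checked with IRR × exp(±1.96 × √(1/E1 + 1/E2)), where E = women × mean person-years × rate. Row 1 has 2,150 and 8,600 women.

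| Loss | Mean person-years | IRR 1 | IRR 1.5 | IRR 2 | Limits matched, all rows |
|---|---|---|---|---|---|
| 15% every year | 3.42 | 0.54–1.84 | 0.89–2.53 | 1.24–3.21 | 3 of 24 |
| 15% once (5 × 0.85) | 4.25 | 0.58–1.73 | 0.94–2.40 | 1.31–3.06 | 22 of 24 |
| Table 3 as printed | | 0.6–1.7 | 1.0–2.4 | 1.3–3.0 | |

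The table fits a single 15% loss better than the annual loss that the text names. This is a separate matter for the sponsor to reconcile.

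**2. Is follow-up fixed?** At 15% a year, 0.85^5 = 0.444, so 55.6% leave before 5 years: 1,823 × 0.556 = 1,014 bazedoxifene women. If 15% applies once, 1,823 × 0.15 = 273 leave. Follow-up is not fixed on either reading.

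**3. Does loss bias the rate or hazard ratio?** I took a true ratio of 2, constant hazards, 5 years and a mean loss hazard of −ln 0.85 = 0.163. A woman with VTE rate v and loss hazard l contributes T = (1 − e^(−5(v+l)))/(v+l) years on average. Each arm's rate is Σ p·v·T / Σ p·T over risk strata.

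- Loss unrelated to risk and equal by arm: 2.00.
- Assumed 30% high-risk women with 3 times the VTE rate and 2 to 4 times the loss, in both arms: 2.00.
- The same dependence in the bazedoxifene arm only: 1.87 to 1.75.
- The same dependence in the bisphosphonate arm only: 2.14 to 2.28.

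For events never recorded, the observed ratio is the true ratio × (1 − f1)/(1 − f2), where f1 and f2 are the unrecorded fractions on bazedoxifene and comparator. With f1 = f2 = 0.2 it stays at 2.00. With 0.3 and 0.1 it is 2 × 0.7/0.9 = 1.56; with 0.1 and 0.3 it is 2 × 0.9/0.7 = 2.57. Where the fractions apply to AT and CR alike, comparing the two shows nothing.

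**4. Does loss shift the crude cumulative incidence ratio?** For a rare event, expected cases per person are about r × T, with T(d) = (1 − (1 − d)^5)/(−ln(1 − d)) at annual loss d.

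- T(0.15) = 0.5563/0.1625 = 3.42 years
- T(0.20) = 0.6723/0.2231 = 3.01 years
- T(0.10) = 0.4095/0.1054 = 3.89 years

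With equal true rates and assumed loss of 20% on bazedoxifene against 15% on the comparator, the ratio is 3.01/3.42 = 0.88. At 10% against 15% it is 3.89/3.42 = 1.14. A true ratio of 2 under 20% against 15% becomes 2 × 0.88 = 1.76. Loss here is unrelated to VTE; unequal amounts are enough. Under the same conditions Kaplan-Meier risk at 5 years estimates 1 − e^(−5 × 0.00174) = 0.0087 in both arms, a ratio of 1.

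**The case against.** The strongest reply is that the sentence is taken out of context. Its reason is that CR disregards non-adherence, and the only censoring named in that paragraph is the AT censoring at discontinuation. For that kind of censoring the SAP is right. The paragraph is also a general account of the two methods; the study-specific rules that follow assign women to their original cohort without repeating the claim. The calendar in SAP Table 1 does leave room for five years per woman. All of this stands, and it is why the sentence needs a limit and not deletion. It does not supply the missing statement about loss.

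A reader might infer that the claimed property simply fails. The documents do not support that. Step 3 shows no bias in the ratio when loss is equal by arm, even if related to VTE risk, and nothing in the documents shows a difference between drugs.

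A reader might also infer that the SAP treats AT and CR as bounds on the truth. It does not: it calls them a plausible range, says that the two trade biases, and hedges on direction. Inference is by 95% confidence intervals and two-sided tests.

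Third, the limits of the data are disclosed: Protocol section 10 names the missing hospital and vital-status information. Missing hospital events are a problem of ascertainment, not of CR as such. That is fair, but the disclosure is not carried into 8.1.4.

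Finally, the crude proportion is not the formal test. SAP 4.2 and 8.2.2 give the comparison to the Cox model, and incidence density, also planned, is not shifted by unequal non-informative loss. This limits the consequence of step 4. Even so, 8.1.2 calls cumulative incidence primary and plans incidence ratios.

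**Conclusion.** The point holds in a limited form. The statement in 8.1.4 is correct for censoring at treatment change and is not assured for loss to follow-up, because event-free women are followed only to last visit or 5 years and deaths are unrecorded. AT and CR rest on the same last-visit records, so their agreement is no evidence against bias from loss.

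For the hazard ratio no size can be given. Bias needs loss or under-recording that is related to VTE and differs by drug, and the documents do not establish this. It is tempting to turn the number of women lost into a number of missing VTEs. The documents give no fraction of losses preceded by an unrecorded event, the 1.74 rate comes from trial placebo groups and not from this database, and the 15% is a planning figure that Table 3 seems to apply only once.

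For the crude cumulative incidence ratio the size is about 0.88 in place of 1, on assumed non-informative annual losses of 20% and 15%. That is modest beside the planned precision (0.6 to 1.8 at a true ratio of 1 for 1,750 against 10,500 women in Table 3). It is a systematic shift, however, and the data already held can correct it.

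**What to change.** - In SAP 8.1.4, limit the sentence on censoring bias to censoring at treatment change. Add that AT and CR both assume non-informative loss at last visit, and qualify the sentence on the plausible range accordingly.
- In SAP 8.1.2 and 8.2.5, compute cumulative risk as Kaplan-Meier risk at fixed horizons (for example 1 and 5 years) with numbers at risk, in place of crude cases over persons.
- Report loss to follow-up and follow-up time by drug cohort and year. SAP 2.1 now promises only the number lost.
- Kaplan-Meier also assumes non-informative censoring, so add a simple bound for unrecorded VTE among women lost: multiply the observed ratio by (1 − f2)/(1 − f1) over a stated grid of unrecorded fractions, and show which combinations would change the conclusion.

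The cost is a few sentences, one table, a standard estimator and a short grid, all on existing data. The downside is a little more analysis and a more guarded conclusion.

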In the determination of person years, the date of first prescription of treatment will be used as a surrogate for time of first exposure to treatment, since the date when the patient had their first treatment for osteoporosis may not be consistently ascertainable. The same definition of person-time ('ever' exposed approach accounting for all person-times of exposure) will be used for all the study endpoints given that they are all chronic diseases or malignancies with potentially long latency periods. If no primary end point occurs during the follow-up period, the duration will be calculated from the start of treatment date to the last patient visit or the end of study period, whichever comes first.

Both methods of calculating incidence rates will be used and the number of patients for whom the date of first treatment for osteoporosis could not be ascertained will be provided as part of the sensitivity analysis of the incidence density approach.

Stratifications by risks of interest (e.g. age, BMI, or selected medical history) will be performed for each outcome and descriptive summaries will be reported. For example, VTE incidence will be stratified according to age as well as by BMI. Other stratifications by medical co-morbidities and other variables of interest will also be performed as appropriate.

Given the rarity of certain malignancies in this population, the incidence rates observed in this study may be small and imprecise. To better characterize the rates obtained in this study, an additional analysis using external reference data for the malignancies will be conducted, i.e. a standardized incidence ratio (SIR). The observed frequency of malignancies in all three treatment groups will be compared with the expected frequency calculated from an age and gender matched population-based reference group (e.g., GloboCan). This SIR of observed versus expected events and 95% confidence interval, will be reported.

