In this study the proportion and demographic and clinical characteristics of patients that switch medications between the study drugs will be reported alongside patients that do not switch medications. Both the AT and CR analytic approaches will be used for all study endpoints and the results reported. In the CR method, if a patient switches from one exposure (study drug) cohort group to another, they will have several treatment durations and will belong to multiple cohort groups but will be analyzed according to their original exposure cohort group (i.e., CR/intent to treat approach). In the AT approach, all exposure cohort groups will be included as a time-dependent variable. With the exposure cohort group as a time-dependent variable, each event will be assigned to the treatment being taken at the time of occurrence. The duration of treatment for each cohort group will be from the date of the first prescription to the date of the event or to the end of treatment, whichever occurs first. The covariates of patients that switched treatment at the time of the event or at the end of follow-up would be considered in this model.

[figure not shown]
The following diagrams shows some example of calculating duration for patients with switched treatments with both the AT and CR approaches.

Figure 2a. Calculating the duration of treatment for patients that switched treatment using the as-treated (AT) approach.

A, B, C: Treatment cohort types. X= Incidence date of primary end point

Figure 2b. Calculating the duration of treatment for patients that switched treatments using the cumulative risk (CR) approach.

A, B, C: Treatment cohort types. X= Incidence date of primary end point

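### Malignancies are counted from the index prescription with no lag, and the as-treated analysis credits each cancer to the drug in use at diagnosis, against the SAP's own latency premise

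*SAP*

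**What the plan says.** SAP 6.2 lists seven malignancy endpoints: the aggregate and six sites (breast, kidney, thyroid, ovary, gastrointestinal tract, lung).

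For women with an event, SAP 8.1.2 states that "person time will equal the sum of days from their first prescription of treatment (index prescription) until the date of the incident condition". The time-to-event analysis in 8.1.4 starts at the same date. Section 8.1.2 applies one 'ever' exposed definition to all endpoints, "given that they are all chronic diseases or malignancies with potentially long latency periods".

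Under 'Patients Switching Medications', SAP 8.1.4 adds two approaches and says "Both the AT and CR analytic approaches will be used for all study endpoints and the results reported". Under CR, a woman stays in her original cohort whatever she takes later. Under AT, "each event will be assigned to the treatment being taken at the time of occurrence", and time on each drug runs "from the date of the first prescription to the date of the event or to the end of treatment, whichever occurs first".

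Protocol 7.2 and SAP 5.4 remove a woman from the analysis of an outcome that she had on record before index, and analyse such women separately. The guaranteed look-back is six months (SAP 2.1), and a condition that is not recorded is taken as absent (SAP 7).

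**The concern.** Section 8.1.2 uses latency to justify following women as ever exposed. If that premise holds, a cancer recorded shortly after the first prescription is unlikely to be caused by the drug, and the drug taken on the day of diagnosis is not obviously the relevant one. Yet early cancers count in full in every analysis, and AT applies current-drug attribution to the endpoints for which 8.1.2 chose the opposite. A cancer found a month after a switch from a bisphosphonate to bazedoxifene becomes a bazedoxifene event. One found soon after stopping bazedoxifene drops out of AT.

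If undiagnosed cancer is equally common in the three cohorts, counting it pulls the hazard ratio towards 1 and hides a late effect. It may not be equal. Bazedoxifene was newly launched, whereas SAP 8.1.4 accepts that bisphosphonate and raloxifene users may have been treated before enrolment. Early time after index therefore does not mean the same thing across the full cohorts. Protocol 7.2 and SAP 8.1.2 already expect some malignancy rates to be small and imprecise, so a few misattributed cases matter.

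**Working it through.** The documents give no cancer rate, latency period or lag, so there is no planned figure to reproduce. The check has two parts.

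**Part 1: does any planned step act as a start lag?**

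- *Exclusion of prior cancers (SAP 5.4).* It removes cancers already in the GP record. It cannot remove those undiagnosed at index, or diagnosed but not entered. SAP 2.1 says hospital information reaches the GP file at later visits and not systematically, so a hospital diagnosis made before index could be entered after it.
- *Record review (Protocol 6.3).* It confirms the diagnosis. It covers breast, ovarian, renal, thyroid and endometrial cancer, not lung or gastrointestinal.
- *30/60/90-day windows (SAP 8.1.3, 8.2.3).* They change exposure after a prescription ends, not when counting starts.
- *Cumulative-exposure categories.* SAP 8.1.3 runs to more than 365 days, but 8.2.2 lists categories only to 180 days. They can show early against late rates, but early cases stay in the main estimates.
- *CR (SAP 8.1.4).* It keeps events after switching or stopping in the original cohort, but still counts from index.
- *Incident-user subgroup (SAP 5.4).* It improves comparability of time since first use but adds no lag.

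None of these is a start lag.

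**Part 2: how much follow-up is involved?**

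Inputs: up to 5 years of follow-up (Protocol 6.1.1, SAP 2.1) and 15% annual loss (Protocol 7.1). Assumed: constant (exponential) loss, equal in both cohorts; a constant cancer rate; lags of 6, 12 and 24 months; a true ratio of 2 that begins only after the lag.

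Person-years per woman to time T are PY(T) = (1 − e^(−kT))/k, with k = −ln(0.85) = 0.1625.

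- PY(5) = (1 − 0.4437)/0.1625 = 3.423
- PY(0.5) = 0.480, share 0.480/3.423 = 14%
- PY(1) = 0.923, share 0.923/3.423 = 27%
- PY(2) = 1.707, share 1.707/3.423 = 50%

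With no loss the shares are 0.5/5, 1/5 and 2/5. With share s and true ratio R after the lag, the average ratio is s + R(1 − s). For 12 months this is 0.27 + 2 × 0.73 = 1.73.

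| Assumed lag | Share, 15% loss | Average ratio | Share, no loss | Average ratio |
|---|---|---|---|---|
| 6 months | 14% | 1.86 | 10% | 1.90 |
| 12 months | 27% | 1.73 | 20% | 1.80 |
| 24 months | 50% | 1.50 | 40% | 1.60 |

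In AT the shares are larger because time on drug is shorter. The documents give no discontinuation rate. Assuming 20%, 40% or 60% a year on top of the loss, with no restarting, k becomes −ln(0.85) − ln(1 − d). The first 12 months then hold 37%, 51% and 66% of on-drug time, and the same true ratio of 2 averages 1.63, 1.49 and 1.34.

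**The case against.** The plan does not ignore latency. 'Ever' exposed time and CR follow women past stopping and switching for up to five years, so both attribution examples above arise only in AT. SAP 8.1.4 openly presents AT and CR as trading one bias for another and giving a plausible range when read together. It also provides for testing proportional hazards and exploring time-varying hazard ratios, although that text is written around the primary endpoint. This stands against two inferences a reader might draw: that no analysis allows for latency, and that the AT malignancy hazard ratio is beyond interpretation. The narrower points remain: CR does not touch early cases, and AT contradicts the premise in 8.1.2.

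A reader might also infer that pre-existing cancers in general are charged to the study drugs. The documents do not support that, because recorded ones are excluded. Only undiagnosed or unrecorded cancers are affected. Nor do the documents show that the work-up before a SERM differs from that before a bisphosphonate, so no false signal from that source can be asserted.

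Finally, section 8.1.2 speaks only of potential latency and gives no duration. The 12-month lag, the step-shaped effect and the ratio of 2 are assumptions. A lag also costs information on sparse endpoints among 1,823 bazedoxifene women (SAP 5.4). That is a fair reason not to make the lagged result the lead analysis, but not a reason to omit it.

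**Conclusion.** The point holds as an inexpensive improvement to secondary endpoints. SAP 8.1.2 and 8.1.4 conflict for malignancies, and no planned analysis removes cancers undiagnosed or unrecorded at index from the rates, hazard ratios or standardised incidence ratio.

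On the assumptions shown, a lag of 6 to 24 months covers 14% to 50% of counted person-time at 15% annual loss and 10% to 40% with no loss. A ratio of 2 that starts only after month 12 is diluted to about 1.73 or 1.80 respectively, and further in AT if discontinuation is appreciable. These figures illustrate dilution when early cancers are equally common in the cohorts. The effect of an unequal share, for instance from earlier treatment of comparator women, cannot be sized from the documents.

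**What to change.** 1. Reconcile SAP 8.1.2 with 8.1.4: name CR/'ever' exposure as the main analysis for all seven malignancy endpoints. Keep AT for malignancies as supportive at most, labelled as assuming no latency.
2. Prespecify two sensitivity analyses for malignancy rates, hazard ratios and the standardised incidence ratio, with person-time and case counting starting 6 and 12 months after the index prescription. Women still under observation and free of that cancer at the lag enter the risk set; the same rule applies to every cohort. State that the lag lengths are a choice and justify them.
3. Show lagged beside unlagged results, in the full comparison and in the incident-user subgroup. A lag from index does not align comparator women already treated before enrolment.

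Cost: SAP wording and reruns on existing data, though more than a single run. Seven endpoints × 2 comparators × 2 populations × 2 lags = 56 hazard ratios for pooled data, or 168 if repeated for Italy, Spain and pooled, plus the rates and the standardised incidence ratio. Lagged intervals are wider. At a constant cancer rate and 15% loss, the log-scale width grows by 1/√0.86 = 1.08 for 6 months and 1/√0.73 = 1.17 for 12 months. The unlagged result is kept, so nothing already planned is lost.
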